2 ELIGIBILITY ASSESSMENT AND ENROLLMENT

2.1 ELIGIBILITY CRITERIA

2.1.1 Inclusion Criteria

For the neoadjuvant cohort, participants must have histopathological documentation of adenocarcinoma of the prostate prior to starting this study and evaluable biopsy tissue (e.g., unstained slides or blocks) available for analysis. If evaluable tissue is not available, the participant must agree to undergo a pre-vaccination prostate biopsy on study.

For the CRPC lead in cohort, if histopathological documentation is unavailable, a rising PSA (see Section [2.1.1.9](#)) and a clinical course consistent with prostate cancer would be acceptable.

2.1.1.1 Age ≥ 18 years. Because no dosing or adverse event data are currently available on the use of PROSTVAC in combination with nivolumab in participants <18 years of age, children are excluded from this study, but will be eligible for future pediatric trials.

2.1.1.2 ECOG performance status of 0 or 1 (see Appendix A, Section [16.1](#)).

2.1.1.3 Participants must not have other active invasive malignancies within the past 2 years (with the exception of non-melanoma skin cancers) (for CRPC cohort only).

2.1.1.4 Participants must be willing to travel to the study site for follow-up visits

2.1.1.5 All participants who have received prior vaccination with vaccinia virus (for smallpox immunization) must not have a history of serious adverse reaction to the vaccine.

2.1.1.6 The effects of PROSTVAC in combination with nivolumab on the developing human fetus are unknown. For this reason men must agree to use adequate contraception (abstinence, vasectomy) or female partner must use (intrauterine device (IUD), hormonal [birth control, pills, injections, or implants], tubal ligation] prior to study entry and for up to 7 months after the last dose.

2.1.1.7 Participants must understand and sign informed consent that explains the neoplastic nature of their disease, the procedures to be followed, the experimental nature of the treatment, alternative treatments, potential risks and toxicities, and the voluntary nature of participation.

2.1.1.8 Participants must have normal organ and marrow function as defined below:

a. hemoglobin	≥ 8 g/dL
b. granulocytes	$\geq 1,500/\text{mcL}$
c. platelets	$\geq 100,000/\text{mcL}$
d. total bilirubin	$< 1.5 \text{ mg/dL}$ (or $\leq 3.0 \text{ mg/dL}$ in participants with Gilbert syndrome)
e. AST(SGOT)/ALT(SGPT)	$\leq 2.5 \times$ institutional upper limit of normal
f. creatinine	$\leq 1.5 \times \text{ULN}$

2.1.1.9 For the lead in cohort:

- Castrate testosterone level ($<50\text{ng/dl}$ or 1.7nmol/L)
- Progressive disease at study entry defined as one or more of the following criteria occurring in the setting of castrate levels of testosterone:

- Radiographic progression defined as **any new** or enlarging bone lesions or growing lymph node disease, consistent with prostate cancer

OR

- PSA progression defined by sequence of rising values separated by >1 week (2 separate increasing values over a minimum of 2ng/ml (PCWG2 PSA eligibility criteria). If participants had been on flutamide, PSA progression is documented 4 weeks or more after withdrawal. For participants on bicalutamide or nilutamide disease progression is documented 6 or more weeks after withdrawal.
- Participants must agree to continuation of androgen deprivation therapy (ADT) with a gonadotropin-releasing hormone agonist/antagonist or bilateral orchiectomy

2.1.1.10 For the neoadjuvant cohort:

1. Participants must be a surgical candidate for radical prostatectomy based on standard workup of PSA, biopsy results, and if necessary supplemental imaging.
2. Participants must have chosen radical prostatectomy as their definitive treatment of choice for management of their prostate cancer as part of their standard of care treatment.
3. No systemic steroid or steroid eye drop use within 2 weeks prior to initiation of experimental therapy. Limited doses of systemic steroids to prevent IV contrast, allergic reaction or anaphylaxis (in participants who have known contrast allergies) are allowed.

2.1.2 Exclusion Criteria

2.1.2.1 Prior splenectomy.

2.1.2.2 The recombinant vaccinia vaccine should not be administered if the following apply to either recipients or, for at least 3 weeks after vaccination, their close household contacts (Close household contacts are those who share housing or have close physical contact):

- persons with active or a history of eczema or other eczematoid skin disorders
- those with other acute, chronic or exfoliative skin conditions (e.g., atopic dermatitis, burns, impetigo, varicella zoster, severe acne or other open rashes or wounds) until condition resolves
- pregnant or nursing women; children under 3 years of age

2.1.2.3 Participants should have no evidence, as listed below, of being immunocompromised:

- HIV positivity due to the potential for decreased tolerance and risk for severe side effects.
- Hepatitis B or C positivity.

2.1.2.4 Concurrent use of systemic steroids or steroid eye drops. This is to avoid immunosuppression which may lead to potential complications with vaccinia (priming vaccination). Nasal, topical or inhaled steroid use is permitted.

2.1.2.5 Participants with known allergy to eggs or to compounds with a similar chemical or biologic composition to PROSTVAC or nivolumab.

2.1.2.6 No prior immune checkpoint inhibitors (e.g., anti-CTLA4, anti-PD-1 or anti-PDL1 are allowed.

Abbreviated Title: Prostvac-Nivo in prostate ca

Version Date: 01.10.2023

2.1.2.7 Other serious intercurrent illness.

2.1.2.8 Participants with a history of unstable or newly diagnosed angina pectoris, recent myocardial infarction (within 6 months of enrollment) or New York Heart Association class II–IV congestive heart failure.

2.1.2.9 Participants with significant autoimmune disease that is active or potentially life threatening if activated.

2.1.2.10 Participants with clinically significant cardiomyopathy requiring treatment.

2.1.2.11 Participants with ongoing toxicities related to prior therapies targeting T cell coregulatory proteins (immune checkpoints) such as anti-PD-1, anti-PD-L1, or anti-CTLA-4 antibody are excluded

2.1.2.12 No transfusion of blood or blood products within 2 weeks and no G-CSF or GM-CSF within 2 weeks prior to initiations of experimental therapy.

2.1.2.13 Contraindication to biopsy or prostatectomy (for neoadjuvant cohort only):

- Bleeding disorders
- Artificial heart valve
- PT/PTT $\geq 1.5 \times$ ULN in participants not taking anticoagulation. Participants on anticoagulation (e.g., enoxaparin, oral anticoagulants) are eligible regardless of PT/PTT. Prior to biopsy, anticoagulation will be held per standard practice.

2.1.2.14 For participants with localized prostate cancer contraindication to MRI:

- Participants weighing >136 kilograms (weight limit for the scanner tables)
- Allergy to MR contrast agent
- Participants with pacemakers, cerebral aneurysm clips, shrapnel injury or implantable electronic devices

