The CDC is the only source of the licensed vaccinia vaccine. The CDC will provide vaccinia vaccine to protect laboratory and other healthcare personnel, whose occupations place them at risk of exposure to vaccinia and other closely related orthopoxviruses, including vaccinia recombinants. The vaccine should be administered under the supervision of a physician selected by the study institution. Revaccination is recommended every 10 years. For instructions on obtaining the licensed vaccinia vaccine, contact Drug Services, National Center for Infectious Diseases, CDC at [contact].

Recombinant Vaccinia Vaccine Patient Care Implications, Contraindications and Potential Complications

Patient Care Implications and Contraindications

Cover vaccination sites with a sterile dry dressing (e.g., Telfa pad). Instruct patients on proper hand-hygiene, sterile dressing care, bathing, laundering of clothing, etc. Treat patient bandages or dressings removed from the vaccination site as infectious waste and dispose in appropriate biohazard containers. Do not administer the recombinant vaccinia vaccine if the recipient, or for at least three weeks after vaccination, their close household contacts (close household contacts are those who share housing or have close physical contact):

- have active eczema or a history of eczema or atopic dermatitis, or Darier's disease.
- have other acute, chronic, or exfoliative skin conditions (e.g., burns, impetigo, varicella zoster, severe acne, contact dermatitis, psoriasis, herpes or other open rashes or wounds), until the condition resolves.
- are pregnant or intend to become pregnant (due to the potential risk of fetal vaccinia); or are breast-feeding (due to the potential risk of contact transmission and inadvertent inoculation). It is currently unknown if vaccinia virus or antibodies are excreted in breast milk. Patients (i.e., vaccinees) should avoid fathering a child for at least 4 months following completion of therapy with the recombinant vaccine.
- are in close contact with children less than 3 years of age (due to the potential risk of contact transmission and inadvertent inoculation).
- are immunodeficient or immunocompromised (by disease or therapy), including individuals with HIV infection.

Additionally, do not administer the recombinant vaccinia vaccine if the vaccinee:

1. has a moderate or severe acute illness, until the illness resolves.

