2. is undergoing topical steroid therapy for inflammatory eye diseases, or undergoing therapy with systemic steroids; potential immune suppression increases risk for vaccinia-related complications.
3. At this time, until a more definitive causal relationship is determined, it is recommended that patients with known CHF or clinically significant cardiomyopathy, not be vaccinated with recombinant vaccinia-based vaccines, due to the potential for development of myocarditis and/or pericarditis.

Although the CDC believes that there is no evidence to conclude that the licensed vaccinia vaccine used in the Smallpox Vaccination Program causes angina or heart attacks, it acknowledges a possible causal relationship between the vaccination and heart inflammation. The CDC continues to study the relationship, but in the meantime, recommends excluding individuals with underlying heart disease from participation in the current Smallpox Vaccination Program. Patients are being immunized with recombinant vaccinia vaccines with therapeutic intent and will be evaluated for cardiovascular risk factors and recent or symptomatic cardiac events per protocol eligibility criteria. Patients will be encouraged to minimize cardiovascular disease risks and encouraged to follow risk reduction according to standard medical practice.

Due to the method of manufacturing (virus grown in primary chicken embryo dermal cells), do not administer the recombinant vaccinia vaccine to patients with a history of allergy to eggs or egg products. Do not administer the recombinant vaccinia vaccine to patients with a history of allergy or serious reaction to prior vaccinia vaccination (e.g., smallpox vaccination).

Potential Complications Associated With Recombinant Vaccinia Vaccination

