- **Myocarditis/Pericarditis:** The CDC has recommended a temporary medical deferral to the voluntary Smallpox Vaccination Program for persons with heart disease or cardiovascular risk factors (March 25, 2003) and issued “interim supplementary information” regarding evidence that smallpox vaccination may cause myocarditis and/or pericarditis (March 31, 2003) in people recently vaccinated with the smallpox vaccine. The cardiac events reported include myocardial infarction, angina, myocarditis, pericarditis, and myopericarditis. Although the CDC believes that there is no evidence to conclude that the licensed vaccinia vaccine causes angina or heart attacks, it acknowledges a possible causal relationship between the vaccination and heart inflammation. The CDC continues to study the relationship, but in the meantime, recommends that individuals with underlying heart disease be excluded from participation in the current Smallpox Vaccination Program. While it is currently not possible to fully evaluate the risk of cardiac events or the risk of myocarditis, pericarditis, or myopericarditis associated with vaccinia vaccination, it is reasonable to inform patients participating in studies using recombinant vaccinia virus of these reports and provide relevant guidance for evaluating these events. Further investigation from the ongoing vaccine program may provide additional data regarding an association or lack of

association with cardiovascular disease. Patients are being immunized with recombinant vaccinia vaccines with therapeutic intent and will be evaluated for cardiovascular risk factors and recent or symptomatic cardiac events per protocol eligibility criteria. Patients will be encouraged to minimize cardiovascular disease risks and encouraged to follow risk reduction according to standard medical practice. At this time the evidence for an association with myocarditis, pericarditis, or myopericarditis seems plausible, but a rare event. If not otherwise excluded, patients with known CHF or clinically significant cardiomyopathy requiring treatment should be excluded from protocol eligibility.

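### Sections 2.1.2 and 14.2 give different contraindications for recombinant vaccinia, most clearly for immunocompromised household contacts, so a man can be eligible under one and barred from dosing under the other

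*Combined protocol and SAP*

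**What the plan says.** **Section 2.1.2 (Exclusion Criteria).** Criterion 2.1.2.2 applies to recipients and, for at least three weeks after vaccination, to their close household contacts. Its three items are eczema, other skin conditions, and "pregnant or nursing women; children under 3 years of age". Criterion 2.1.2.3 reads "Participants should have no evidence, as listed below, of being immunocompromised", and the list that follows has two entries: "HIV positivity due to the potential for decreased tolerance and risk for severe side effects" and "Hepatitis B or C positivity". Criterion 2.1.2.8 excludes, among other cardiac conditions, "New York Heart Association class II–IV congestive heart failure".

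**Section 14.2 (Recombinant Vaccinia, patient care implications and contraindications).** This forbids giving the vaccine when listed conditions apply to the recipient or, over the same period, to close household contacts. One of the conditions is that they "are immunodeficient or immunocompromised (by disease or therapy), including individuals with HIV infection". On the heart, it recommends that "patients with known CHF or clinically significant cardiomyopathy, not be vaccinated with recombinant vaccinia-based vaccines". Its later paragraph on myocarditis and pericarditis says that "patients with known CHF or clinically significant cardiomyopathy requiring treatment should be excluded from protocol eligibility".

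**The concern.** Section 2.1.2 decides who enters the trial, and Section 14.2 says who may be given the vaccine. If the first is narrower than the second, a man can be enrolled properly and then found ineligible for the week 0 dose. If nobody returns to Section 14.2 at dosing, he may be vaccinated against the protocol's own instruction. The household-contact item also protects people who are not in the trial and have not consented to it. Endpoints, sample size and analysis are not affected.

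**Working it through.** No arithmetic applies. The check sets the two sections side by side, item by item.

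| Item | Section 2.1 | Section 14.2 |
|---|---|---|
| Contacts: eczema, other skin disease, pregnancy or nursing, children under 3 | Present in 2.1.2.2 | Present |
| Contacts: immunocompromised | Absent | Present: "are immunodeficient or immunocompromised (by disease or therapy), including individuals with HIV infection" |
| Participant: immunocompromised | HIV, hepatitis B or C (2.1.2.3), plus partial cover elsewhere | General, with HIV given as one example |
| Participant: heart failure | "New York Heart Association class II–IV congestive heart failure" | Known CHF, no class stated |

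**1. Household contacts.** The two lists open with nearly the same sentence and cover the same people over the same period. Four of the five categories in Section 14.2 have a counterpart in 2.1.2.2. The wording differs at the edges (Section 14.2 also names Darier's disease and intended pregnancy), but the categories correspond. The fifth category, immunocompromise, has no counterpart for contacts. Criterion 2.1.2.3 is limited to participants, and no other inclusion or exclusion criterion refers to contacts. The catch-all 2.1.2.7 concerns illness in the participant.

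**2. Participants.** Criterion 2.1.2.3 ties immunocompromise to its own short list. Other criteria extend the cover: prior splenectomy (2.1.2.1), systemic steroids and steroid eye drops (2.1.2.4), significant autoimmune disease (2.1.2.9), and an undefined reference to serious intercurrent illness (2.1.2.7). Non-steroid immunosuppressive treatment and immunodeficiency other than the listed infections remain unnamed. A man on a non-steroid immunosuppressant without significant autoimmune disease is an example: no named criterion stops him, and Section 14.2 does.

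**3. Heart failure.** Criterion 2.1.2.8 leaves NYHA class I unmentioned, and 2.1.2.10 deals with cardiomyopathy, not CHF. Section 14.2 has two relevant statements for study patients. One is a recommendation against vaccinating ("patients with known CHF or clinically significant cardiomyopathy, not be vaccinated with recombinant vaccinia-based vaccines"). The other concerns eligibility ("patients with known CHF or clinically significant cardiomyopathy requiring treatment should be excluded from protocol eligibility"). Neither gives a class. In the second, the phrase about needing treatment may attach to CHF as well as to cardiomyopathy; the first has no such phrase.

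**The case against.** The strongest reply is that Section 14.2 is operative protocol text. Its prohibition on dosing stands whatever Section 2.1.2 says, so a reader who infers that the protocol permits vaccination of a man with an immunocompromised household contact goes too far. That is right: enrolment under 2.1.2 does not authorise a dose that Section 14.2 forbids. The mismatch remains, because the same man is then eligible in one section and barred in the other.

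Three other strong readings are tempting, and the documents do not support them.

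- *That 2.1.2.3 is the whole screen for participant immunocompromise.* It is not. The criteria listed above cover part of the ground, and 2.1.2.7 gives the investigator discretion over the participant. The gap is the narrower one described.
- *That Section 14.2 flatly bars heart failure of every class.* It states no class, its verbs are advisory, and the treatment qualifier is ambiguous in one place. Both passages also say that patients will be assessed for cardiac risk under the protocol's eligibility criteria, which sends the question back to Section 2.1. This is a discrepancy to settle, not a clear admission of barred men.
- *That the complication rates in Section 14.2 measure the harm.* They come from smallpox vaccinees generally and do not isolate any added risk from these criteria. Taken at face value, the quoted contact-transmission rate of 27 per million gives 29 × 27/1,000,000 ≈ 0.0008 expected events at the accrual ceiling. Section 14.2 adds that contact transmission rarely leads to progressive vaccinia or encephalitis.

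**Conclusion.** The inconsistency is real, and it is firmest for household contacts: a category that Section 14.2 treats as a bar to dosing is missing from the eligibility criteria. The participant mismatch holds for non-steroid immunosuppression and unlisted immunodeficiency. The heart-failure mismatch holds as a difference in wording, class-limited in one section and unqualified by class in the other.

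Its size is these three categories. The documents do not say how many men would fall into them, and the expected number of vaccinia complications among at most 29 participants is very small. The case for correcting it is that one protocol should not give two answers about a live virus when participants and unconsented third parties bear the risk.

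The conclusion rests on Sections 2.1 and 14.2 as written. It takes no position on Appendix B, which was not available, or on which of the conflicting rules is clinically right.

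**What to change.** Reconcile 2.1.2.2, 2.1.2.3 and 2.1.2.8 with Section 14.2 so that a single list of vaccinia contraindications governs both enrolment and dosing, and have each section refer to it. The list should state:

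- whether an immunocompromised household contact is a bar;
- whether participant immunocompromise means the listed infections or a general definition, and if general, how it relates to 2.1.2.1, 2.1.2.4, 2.1.2.7 and 2.1.2.9;
- which NYHA classes of CHF are a bar, and whether a need for treatment is part of the test.

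The choice among these belongs to the sponsor and the investigator. The cost is a wording amendment and, if the broader list is kept, a few more screen failures.

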2.1.2.15 History of radiation proctitis (for lead-in CRPC cohort only)

2.1.3 Recruitment Strategies

This protocol may be abstracted into a plain language announcement posted on NIH websites and on NIH social media platforms. Participants may also be recruited from the current patient population at NIH.

Screening Evaluation

2.1.4 Screening activities performed after a consent for screening has been signed

The following activities will be performed only after the subject has signed the consent for study # 01-C-0129 (Eligibility Screening and Tissue Procurement for the NIH Intramural Research Program Clinical Protocols) on which screening activities will be performed. Assessments performed at outside facilities or on another NIH protocol within the timeframes below may also be used to determine eligibility once a participant has signed the consent.

2.1.4.1 For Lead-in CRPC Cohort

- Pathological confirmation of diagnosis. May be obtained any time prior to enrollment.

- The following parameters will be obtained within 8 weeks prior to start of enrollment:
 1. HIV test
 2. Hepatitis B and C
 3. Height
- The following parameters will be obtained within 4 weeks prior to start of enrollment:
 4. Tc-99 whole-body scintigraphy
 5. CT (or MRI may be substituted at investigator's discretion) of chest, abdomen and pelvis
- The following parameters will be obtained within 16 days prior to start of enrollment:
 6. History and physical examination including vital signs
 7. ECOG performance status
 8. Complete blood count plus differential and platelet count
 9. Hepatic (alkaline phosphatase, AST, ALT, total bilirubin, direct bilirubin), Mineral (albumin, calcium, magnesium, phosphorus) and Acute Care (sodium, potassium, chloride, bicarbonate, creatinine, glucose, BUN, eGFR) Panels
 10. Serum lipase
 11. Amylase
 12. Serum PSA
 13. Testosterone level
 14. HIV serology (within 60 days prior to enrollment)
 15. Serology for hepatitis B and C (within 60 days prior to enrollment).
 16. TSH
 17. PT/PTT

2.1.4.2 For neoadjuvant cohort

- Pathologic Confirmation of Diagnosis by the Laboratory of Pathology, CC, NIH, or Walter Reed National Military Medical Center (if specimen is available).
- Participants that do not have previously collected biopsy material available will be asked to undergo a prostate biopsy.
- The following parameters will be obtained within 35 days prior to start of enrollment:
 - History and Physical Exam, including height measurement
 - Performance Status Evaluation
 - EKG
 - Laboratory Evaluation
 - CBC with differential and platelet count
 - Acute care panel
 - Hepatic Panel
 - HIV serology (within 60 days prior to enrollment)
 - Serology for hepatitis B and C (within 60 days prior to enrollment).
 - Lipase

Abbreviated Title: Prostvac-Nivo in prostate ca

Version Date: 01.10.2023

- Amylase
- TSH
- Serum PSA
- PT/PTT

